1.0. Research Study methods

This project will conduct a randomized comparative effectiveness clinical trial with 89 Veterans with schizophrenia or schizoaffective disorder (SZ/SZA). In addition family members or other informal support persons will be invited to formally join the study with each Veteran with SZ/SZA who consents to join the study. These subjects will be randomized into one of two study arms: 1) the Daily Support Website (DSW), this group will receive access to the DSW intervention that includes three facilitated group forums, Ask Our Experts Your Questions, the Questions and Answers Library of previously asked and answered questions, educational materials, tutorials and self-help guides, libraries, and community resources lists; and 2) in-person Multi-Family Group (MFG). This is the standard in-person method for providing multi-family psycho-education to veterans with schizophrenia and their supporters (e.g., family members) in the VA. This group will receive the standard and manualized MFG treatment provided by the VA, it will be provided by trained clinicians, and supervised by those who provide supervision in the VA. In both study arms, participants will receive all treatment as usual (TAU). In the DSWDSWDSW arm, as needed Veterans can receive a new or refurbished computer and Internet access at home.

All Investigators and staff on the research team will have completed educational training required by the VA.

Recruitment

Veterans will be recruited from the two VA campuses in the Pittsburgh area, University Drive, and H.J.Heinz, and five Community Based Outpatient Clinics (CBOCs). Veterans will be randomly assigned to the two treatment arms, and will be stratify by: distance from/difficulty traveling to the VA medical center (<40 min. or do not have significant transportation barriers, vs. ≥ 40 min. or have significant transportation barriers); number of prior psychiatric hospitalizations (<5 vs. ≥ 5); and gender. The study statistician will generate randomization tables prior to beginning recruitment, and these will be used to assign participants to one of the arms. Flyers describing the study will be available at each site.

Staff at the two VA campuses in the Pittsburgh area, University Drive, and H.J.Heinz, will inform eligible/potentially eligible Veterans and family about the study. If a Veteran is interested, the Veteran can call a recruiter, a staff member can provide a study recruiter with contact information if a waiver is authorized by the Veteran, and the recruiter will follow-up with the Veteran, or alternatively a Veteran could set a time to meet with a recruiter to learn more about the study.

Participants will also be recruited through clinician referrals and review of clinic rosters. A partial Health Insurance Portability and Accountability Act waiver will be obtained to allow review of individuals' charts in order to determine potential eligibility prior to a Veteran's clinic appointment. The charts of potentially eligible Veterans will be reviewed to confirm that each meets study criteria. Eligible individuals will then be approached at their clinic appointments to discuss the study.

During recruitment a research staff member will review and eligibility criteria with veterans. These are: have a DSM-V diagnosis of schizophrenia or schizoaffective disorder; are 18-70 years old; are not in another family treatment, and; are able to speak and read English at the 5th grade level.

To enhance recruitment of Veterans we will utilize the REORDER intervention (HSR&D grant IIR 04-255, [name] PI and consultant to this project, and [name] a Co-Investigator on the REORDER study, and a Co-Investigator on this project). REORDER is a method that is used during the recruitment process, prior to consent. It has been shown to increase recruitment of veterans with a severe mental illness (SMI) into treatment studies and increase their willingness to agree to have their family join the treatment as well. REORDER has two phases: the first focuses on the Veteran, the second involves meetings with the family. We will utilize the first or Veteran phase, with the option to also use the second or “family phase” as needed, for example, depending on whether it is needed to encourage a family to join treatment with a veteran. In Phase I, which can have three or more sessions, a Veteran meets with an appropriately trained research staff member who provides evidence about family involvement in treatment, and helps the veteran to consider the role of family involvement in his/her recovery. In this phase the research staff member will identify the resources of in-person MFG or DSW that might help the Veteran achieve his/her goals. This should improve the acceptability of receiving treatment, and willingness to invite family to participate. In Phase 2, the same information and approach is used when meeting with family members.

Consenting

Consenting will occur in face-to-face meetings between a study staff recruiter and a veteran, a veteran’s family member/supporter or a Veteran and his/her family member/supporter. During the consenting process, if a potential participant decides that one or more of the conditions of the study are unacceptable, we will note the issues for which a person voiced concern to allow us to track the various types of concerns voiced during recruitment. These data will allow us to explore the acceptability of the two treatment methods and various components of the interventions, problem areas for Veterans, and areas where possible adjustments might lead to more widespread acceptability of both of these two approaches to providing this treatment. This information could be valuable to the design of both in-person and e-health models of treatment delivery.

Identification of Family member/Support person for study participation and data collection

A standard question will be asked of the Veteran to identify the person who is their primary family supporter or other primary support person. To verify this, a similar question will be asked of the support person identified. If there is a tie between two or more support persons (e.g., family members), it will be the person who spends the most face-to-face time with the Veteran who will be used as the “primary” support person for data collection.

Recruitment of Family/Support persons

To recruit family members and support persons, the Veteran will be asked to identify appropriate persons (family, other support persons). A brochure explaining the study will be sent to such persons, either by mail or the Veteran will provide it to him or her. Staff will also tell family about the study when they see them at a clinic, or talk with them as part of standard clinical care over the telephone. Family and support persons will be provided with a number and contact information of a study recruited, who they can get in touch with for additional information concerning the study. If they are interested in participating they will be formally consented to join the study by research staff. The primary support person/family member for the veteran must be ≥ 18 years old and able to speak and read English at the 5th grade level.

1. After consenting, and then baseline data collection, participants will be assigned to one of two treatment arms. Those in each arm will receive a different form of multi-family psychoeducation treatment. One arm will receive Multi-

Family Group (MFG). This treatment is provided in in-person group meetings that occur every other week for one year. The other arm will receive the treatment for one year via the Daily Support Website.

a. Multi-Family Group (MFG). Participants assigned to the Multi-Family Group arm will receive the standard Multi-Family Group treatment provided by the VA. The treatment includes: individual participant and individual family meetings with the study clinician(s) who is providing the MFG treatment, using in-person and phone meetings; attending a multi-family group educational meeting (the Psychoeducational Survival Skills Workshop) that will be attended by the veterans and supporters who will be in a particular group, the clinicians leading the treatment, and potentially other experts who have specific content expertise and will provide brief presentations on a particular educational topic (e.g., how medications act to treat schizophrenia); and bi-weekly meetings of the group that will be led by the two clinicians. The study clinicians will be supervised by the study Investigators.

The MFG model begins with two participant engagement activities. The first activity is joining sessions where the therapist meets with each individual participant (veteran, and when present supporter), to develop a collaborative relationship and discuss MFG. These meetings can involve both individual participant meetings as well as joint family meetings (i.e., veteran and his/her supporters). The number of meetings varies by individual and family need (as jointly determined by the therapist and the participants). Following these meetings with the participants who will form an individual in-person group, a Psychoeducational Survival Skills Workshop (PSSW) is held. The PSSW varies in length from 2 to 7 hours, depending on the educational needs of the participants and the amount of time they are able to tolerate a meeting. The PSSW includes educational presentations on schizophrenia, and group discussions. The specific educational topics are chosen and adapted based on the needs of the participants as determined by the therapists during the joining sessions. Once the PSSW is held the multi-family treatment sessions begin on a bi-weekly basis. Each meeting is structured around reviewing the results of a previous meeting's effort to solve a member's problem and then identifying one new problem of a group member to be solved via the group problem solving process.

b. Daily Support Website (DSW). Participants assigned to be in the Daily Support Website arm will receive access to this website and its associated functionalities. The DSW provides the following five resources. (1) Three on-line group forums. One for persons with SZ/SZA only (the SZ/SZA peer group), one for family/supporters only, and a combined group for both persons with SZ/SZA and support persons. In each group the therapists emphasized discussions that focus on problem-solving, alleviating stresses, and encouraging peer interactions. (2) Educational materials and tutorials. (3) A section to ask questions and receive an answer from the therapists associated with the project. (4) A library of previously asked and answered questions. (5) A list of community resources. Those who do not have a computer will have a computer (e.g., laptop, touch pad, or chrome book) provided to them, and Internet service, both free of charge to allow them to participate in the intervention. After their participation is over they will return the equipment.

The DSW treatment begins with two participant engagement activities. The first activity is joining sessions where the study therapist(s) meets with each individual participant (veteran, and when present supporter). These meetings can be in-person, via phone or over the internet. The purposes of the meetings are to develop a collaborative relationship, discuss the DSW, facilitate comfort with the e-health approach to receiving treatment, and develop an individual goal or identify a current 'issue' or 'complaint' that is bothering the individual. These meetings can involve both individual participant meetings as well as joint family meetings (i.e., veteran and his/her family/supporters). The number of meetings varies by

individual and family need (as jointly determined by the therapist and the participants). During the initial treatment period a therapist or research staff member may call a participant to ensure there are no issues with accessing the DSW, such as problems with equipment or lack of understanding of one or more aspects of using the DSW.

2. Participant Data collection. Outcomes data will be collected at scheduled time points of baseline (0), 6, 12, and 15 months. Each of these sessions is estimated to take about 2 hours. The data to be collected is described in Table 4.1.

Table 1.1. Data collection

Information	Measure

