1.2.10. Treatment Satisfaction. The Client Satisfaction Questionnaire (CSQ-8) will be used to assess satisfaction with treatment. The CSQ-8 is used worldwide to assess client/patient satisfaction with services. It has good internal consistency (coefficient alpha 0.86 to 0.94) and concurrent validity.

1.2.11. Participant Treatment Exposure. We will log each subject's contact with treatment in each study arm. In the in-person arm this will include session attendance and any other contact with the therapists relevant to the treatment outside of the sessions. The same will be done for the DSW arm. This will also include any usage of the website, which will be logged on the server for each participant.

1.1.12. Intervention Initiation: DSW and in-person MFG. Treatment initiation will be defined as those that consent to participate in the study and then begin treatment. For both treatments two components of initiation will be tracked. First, will be participating in the Joining Sessions, then will be participation in the PSSW.

1.1.13. Intervention Engagement: DSW and in-person MFG. We will assess the number of Veterans who become engaged in the two treatments. Based on established standards for defining therapeutic treatment engagement as returning for treatment after the intake or initial session, we have previously defined initial engagement in DSW as participating in the PSSW and then using DSW to participate in an on-line group forum (e.g., logging on to the website and posting a ‘new member’ introduction) and an educational activity (e.g., reading an article). For in-person MFG intervention engagement will also be participating in the PSSW and then attending a first in-person group meeting.

1.1.14. Intervention Attendance/Commitment: DSW and in-person MFG. The number of weeks that participants attend each treatment will be assessed. For DSW this is defined as logging on to the website for at least 15 minutes in a week. For in-person MFG meetings are every other week, so each attendance covers two weeks.

1.1.15. Intervention Drop-out: DSW and in-person MFG. We will track the number of participants who drop-out of treatment in both arms. We will track those who officially drop-out of the study, and those who indicate that they no longer wish to receive treatment, though they may not drop-out of the study.

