42 and 47 subjects per treatment arm respectively (n=89 total) represent the number of Veterans that need to complete their assigned interventions. We expect that the non-completion rate for the in-person MFG arm to be $\leq 33\%$ and DSW arm to be $\leq 10\%$. Given these estimates 70 in person MFG subjects will be enrolled and 47 DSW subjects, for a total of 117 to account for attrition and non-completers. Sample size calculations used PASS (2008, NCSS, LLC, Kaysville Utah.).

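### Section 1.0 gives 89 Veterans as the randomised total, but Section 1.8 makes 89 the completer target and enrols 117 (70 MFG, 47 DSW); the two must be reconciled and the allocation ratio stated

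*Combined protocol and SAP*

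**What the plan says.** Section 1.0 opens with "This project will conduct a randomized comparative effectiveness clinical trial with 89 Veterans with schizophrenia or schizoaffective disorder (SZ/SZA"), and shortly afterwards adds "These subjects will be randomized into one of two study arms". Under Recruitment in the same section, "The study statistician will generate randomization tables prior to beginning recruitment". That text lists three stratification factors but gives no allocation ratio and no table length. The numbered item that follows the recruitment of support persons fixes the order of events: "After consenting, and then baseline data collection, participants will be assigned to one of two treatment arms".

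Section 1.8 gives 89 another meaning. It requires 42 DSW and 47 MFG Veterans, and says these numbers ("n=89 total) represent the number of Veterans that need to complete their assigned interventions"). It allows for up to 33% non-completion in MFG and up to 10% in DSW, and concludes: "Given these estimates 70 in person MFG subjects will be enrolled and 47 DSW subjects, for a total of 117".

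Two other places bear on the consequence. Section 1.1.15 (Intervention Drop-out) separately tracks "those who indicate that they no longer wish to receive treatment, though they may not drop-out of the study". Section 1.7 (Data Analysis) keeps partially observed subjects in the mixed-effect regressions, but does not say who enters the initial mean-ratio tests at 12 and 15 months.

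**The concern.** The figure 89 is the number randomised in one section and the number completing treatment in another. With non-zero attrition it cannot be both. Nor does it help to read 117 as a pre-randomisation count: it is broken down by arm, arms exist only after consent and baseline, and the 28 extra Veterans cover failure to complete an assigned intervention at arm-specific rates.

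The randomisation tables are to be made before recruitment starts, so their length and ratio must be known by then. The text does not settle either. A team working from Section 1.0 would stop 28 Veterans short of Section 1.8's enrolment, and would reach the required 89 completers only if nobody left treatment, although Section 1.8 allows for up to a third of the MFG arm doing so. The stated power above 80% would then depend on how many non-completers still provided 12- and 15-month outcomes.

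**Working it through.** **Inputs**
- Section 1.8: 42 per arm before the clustering correction; about 10% inflation for MFG, giving 46–47; margin 1.2 at CV 0.3; one-sided alpha 0.025; power above 80%; non-completion at most 33% (MFG) and 10% (DSW); enrolment 70 + 47 = 117.
- Section 1.0: 89 Veterans, randomised.
- Assumptions not in the plan: true ratio of means 1, and log-normal outcomes.

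**Step 1. Reproduce the plan's enrolment figure.** Enrolled = completers / (1 − non-completion).
- MFG: 47 / 0.67 = 70.1, so 70.
- DSW: 42 / 0.90 = 46.7, so 47.
- Total: 70 + 47 = 117, as stated. Difference from Section 1.0: 117 − 89 = 28.
- Implied allocation: 70 / 47 = 1.49, or about 3:2 MFG to DSW.

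**Step 2. Reproduce the plan's power.** On the log scale, SD = √ln(1 + 0.3²) = 0.2936 and the margin is ln 1.2 = 0.1823. The MFG number is divided by 1.1 for clustering. With 42 DSW and 47 MFG completers:
- SE = 0.2936 × √(1/42 + 1/42.73) = 0.0638.
- Noncentrality = 0.1823 / 0.0638 = 2.86.
- Power (noncentral t) = 81%, in agreement with the stated figure.

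With 117 randomised and maximum attrition, completers are 47 × 0.90 = 42.3 and 70 × 0.67 = 46.9, and power is again 81%.

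**Step 3. Suppose only 89 are randomised.** The ratio is not stated, so three splits are shown. The first two columns assume that non-completers supply no outcome data.

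| Split DSW:MFG | Maximum attrition (10%, 33%) | Half those rates (5%, 16.5%) | All 89 supply data |
|---|---|---|---|
| 1:1 | 40.1 + 29.8 = 69.9; 69.2% | 42.3 + 37.2 = 79.4; 75.7% | 80.7% |
| 42:47 | 37.8 + 31.5 = 69.3; 69.5% | 39.9 + 39.2 = 79.1; 75.8% | 80.6% |
| 47:70 | 32.2 + 35.7 = 67.9; 69.1% | 34.0 + 44.5 = 78.4; 74.9% | 79.5% |

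Each cell gives the number analysed (DSW + MFG, added before rounding) and then power. For example, the 42:47 split at maximum attrition has SE = 0.2936 × √(1/37.8 + 1/28.63) = 0.0727, and 0.1823 / 0.0727 = 2.51, which gives 69.5%.

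**Step 4. Check whether the ratio matters.** If 117 were split equally, MFG completers at 33% attrition would be 58.5 × 0.67 = 39.2, below the 47 required. DSW completers would be 58.5 × 0.90 = 52.7, and overall power would stay near 81%. An unstated ratio therefore puts the per-arm target at risk, but not the power.

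**The case against.** The best defence is that Section 1.8 explains itself. It says what 89 is and what 117 is, by arm, so Section 1.0 can be read as an introductory sentence carrying an unlabelled completer figure. On that view this is a labelling slip, and if 117 are enrolled nothing is lost. It is fair that Section 1.8 is clear and contains no arithmetic error. But it does not correct Section 1.0, which ties 89 to a randomised trial and says nothing of completion. The sentence about randomising these subjects does follow one about family members, so its reference is a little loose; the opening sentence makes the link without it.

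The power loss is also conditional, and that stands. The 69–70% needs attrition at the ceiling of rates given as upper limits, and no outcome data from anyone who stops treatment. The plan's rates concern completing the intervention, not the assessments.

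The result further depends on the margin and CV. Hypothesis 1.1 in Section 1.7 allows ratios from 1.20 to 1.47 depending on CV. By the same method at CV 0.5 and margin 1.47, 68–70 completers still give about 90%, against 96% with 89. At CV 0.5 and margin 1.2, even 89 completers give only about 42%. The choice of margin and CV thus moves power more than 89 versus 117 does.

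Lastly, the 3:2 ratio can be inferred from the arm sizes. Its absence from the randomisation text is a reporting gap rather than a contradiction.

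**Conclusion.** The concern holds. Two current passages give incompatible randomised totals, 89 and 117, and the allocation implied by 70:47 is never stated. Section 1.8 is internally consistent, and following it gives about 81% power. Following Section 1.0 would leave 68–70 completers at maximum attrition and power between 69–70% (completers only) and about 80–81% (all 89 observed), so the cost ranges from about 11 points to almost none. The 11-point loss is a worst case. These figures rest on margin 1.2, CV 0.3, one-sided 0.025, the plan's 10% MFG inflation, a true ratio of 1 and a log-normal model. The contradiction itself depends on none of them.

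**What to change.** State the randomised number, the completer number and the allocation ratio separately, and use the same figures in both sections.

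- **If Section 1.8 is the operative plan** (the option that fits its own sample-size reasoning), Section 1.0 should say that 117 Veterans will be randomised, 70 to MFG and 47 to DSW, to yield 89 completers. The randomisation tables should be built for that total and ratio. This is 28 more Veterans than Section 1.0 states, but none beyond Section 1.8.
- **If 89 is the randomised total**, Section 1.8 should drop the 117 and restate expected completers (about 69 at maximum attrition). It should also restate power at margin 1.2 and CV 0.3: about 70% on completers only, rising to about 81% if non-completers supply outcome data. This needs no extra patients, but on completers only it falls below the plan's own power target, and the text should say so.

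In either case, Section 1.7 should say whether the 12- and 15-month ratio tests use completers only or everyone with outcome data, since that decides which power figure applies. The cost is wording, plus the length and ratio of the randomisation tables.

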1.8. Power, Sample Size, with Estimation of Missing Subjects Follow-up

The primary Veteran outcomes are SAPS and SANS, and family outcome is caregiver burden. Note, for these outcome measures higher scores indicate worse symptoms. The equivalence ratio that will be tested is the mean of DSW/mean of in-person MFG. For both Veterans and family members we plan for the study to detect equivalence ratios of 1.2 for the two measures of psychotic symptoms (SAPS and SANS) and caregiver burden. In these hypotheses tests the null hypotheses are that DSW outcome means are inferior to MFG. The ‘alternative’ hypotheses are that outcomes means in the DSW arm are equivalent to outcomes in the in-person MFG arm. If as an example, the symptoms are higher in the DSW arm, and thus the ratio of the mean of the DSW arm to the mean of the in-person MFG arm exceeds 1.2 (i.e. mean of DSW > mean in-person MFG by 20% or more) we will accept the null hypothesis that the mean of DSW > mean of in-person MFG, and that DSW is not as effective as in-person MFG. Any ratio of DSW/MFG that is < 1.2 will cause us to reject the null hypothesis and accept the alternative that they are equivalent. For the caregiver burden scale the equivalence ratio that leads to rejection is slightly smaller, it is 1.17 because there is only 1 primary measure. With 42 subjects per treatment arm, power is >80% with one tailed alpha =0.025 to detect equivalence ratios of 1.2 (and above). For testing whether DSW is superior to in-person MFG on the illness symptom measures we can reverse the ratio and test whether (mean of in-person MFG/mean DSW) is > 1.20. For these sample size calculation we used reported data to estimate the coefficients of variation (CV) of the scales. CVs commonly range from 0.3-0.5 and within this range there were differences in the calculated equivalence ratios. For alpha =0.025, and CV equal to 0.3 the equivalence ratio bound was 1.20 with an increase to 1.29 for a CV of 0.5.

For the in-person MFG arm a correction for nesting of subjects in a group is needed, which increases the number of subjects required. If it is assumed that this dependency is 0.01 and groups are of size 6-8 then variance inflation factor is on the order of 10%, resulting in 46-47 subjects being needed for the in-person MFG arm. Because DSW is available separately for each Veteran and family member it is not necessary to increase the 42 subjects needed for this group. The

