1.7. Data Analysis

Overview. Initially we will assess whether our stratified randomization procedures yielded groups equivalent in groups on the stratification factors and other demographic and clinical variables. These analyses will be completed with chi-square statistics for categorical variables (or Fisher Exact statistics as needed for small ns) and t-tests for continuous measures (or Kruskal-Wallace tests if there are serious deviations from normality on these variables). Our initial analyses of the primary dependent measures for Veterans, the SAPS and SANS, and for family members/supporters, Caregiver Burden, will test the mean ratios at time points 12 and 15 months to test for non-inferiority. Then the analyses will be move to mixed effect regressions with the primary effects of interest the interaction between time of measurement and treatment group. The use of mixed effect regression allows us to include subjects with partially complete data, e.g. missing the 6 month interview but have baseline, and 12 month interview data available (see below). Prior to the regression analyses we will also check to insure that the continuous measures (SAPS, SANS, Caregiver Burden) are normally distributed. If these assumptions are violated we will identify appropriate transformations to normalize these outcomes or use different forms of the outcome variables and regression techniques that do not require normality to be appropriate. Also of interest will be differences between completers vs. non-completers across the 2 groups as well as within groups (see specifics below under Aims 1 and 2).

1.7.1. Specific Aim 1

We will conduct a 2-arm, non-inferiority randomized comparative effectiveness trial of DSW and in-person multi-family MFG. We will compare changes in severity of Veterans' of psychiatric symptoms (i.e., positive and negative symptoms), and caregiver psychological burden, during the treatment period and then 3-months post-treatment.

Hypothesis 1.1. Veterans participating in DSW will do as well or better than those participating in in person MFG with an equivalence ratio of 1.20-1.47 (depending on the coefficients of variance of the measures assessed) at time points 12 and 15 months.

Hypothesis 1.2. Family caregivers participating in DSW will do as well as or better than those participating in in-person MFG with an equivalence ratio of 1.17-1.29 (depending the coefficient of variance of the measure assessed) at time points 12 and 15 months.

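### The >80% power for caregiver burden rests on 42 supporters per arm, but 42 counts completing Veterans and the design secures no number of supporters

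*Combined protocol and SAP*

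**What the plan says.** Caregiver burden is the primary family outcome (section 1.8 and the data collection table). It has its own non-inferiority hypothesis at 12 and 15 months (Hypothesis 1.2 in section 1.7.1).

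Section 1.8 treats the two populations together: "For both Veterans and family members we plan for the study to detect equivalence ratios of 1.2". It gives more than 80% power with 42 subjects per arm at a one-tailed alpha of 0.025. For caregiver burden it then sets a smaller ratio: "it is 1.17 because there is only 1 primary measure". Hypothesis 1.2 gives a range of 1.17 to 1.29, depending on the coefficient of variation. On variability, section 1.8 says that "CVs commonly range from 0.3-0.5".

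The in-person arm is raised to 47 for nesting. The 42 and 47 "represent the number of Veterans that need to complete their assigned interventions". They are inflated for non-completion (10% DSW, 33% MFG) to 47 and 70, a total of 117.

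Section 1.0 says that "family members or other informal support persons will be invited to formally join the study". The Veteran eligibility list under Recruitment does not require a supporter. The joining sessions in both arms (items 1a and 1b) are described for "veteran, and when present supporter". One primary support person per Veteran is used for data collection. Neither an expected supporter uptake, nor a supporter drop-out rate, nor a target number of supporters is stated anywhere.

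**The concern.** The power statement for a primary outcome uses a count of a different population. A Veteran can be enrolled, randomised and complete treatment with no supporter in the study, and that Veteran adds nothing to the caregiver-burden comparison. A second relative of another Veteran cannot fill the gap, because only the primary supporter is used for data collection.

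The inflation to 117 covers Veteran non-completion, and with it supporters who leave together with the Veteran. It does not cover Veterans without a supporter, or supporters who leave while the Veteran stays.

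A non-inferiority test with too few subjects tends to end inconclusively. Hypothesis 1.2 could fail because supporters were few and not because DSW is worse, although the plan had stated power above 80%.

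**Working it through.** **Inputs from the documents.** Section 1.8: 42 per arm, ratio 1.20, caregiver ratio 1.17, one-tailed alpha 0.025, CV 0.3 (the value behind the 1.20 bound), ICC 0.01, groups of 6 to 8, 42 and 47 completing Veterans, 47 and 70 enrolled.

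**Assumptions.** The true ratio is 1. Supporter uptake *u* is the same in both arms. Neither figure is in the documents.

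**Formula.** On the log scale, σ = √ln(1 + CV²) and SE = σ√(1/n₁ + 1/n₂). Power comes from the noncentral t with noncentrality ln(R)/SE and n₁ + n₂ − 2 degrees of freedom.

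**Step 1: the plan's figure.**
- σ = √ln(1.09) = 0.2936.
- SE = 0.2936 × √(2/42) = 0.0641.
- ln(1.20)/SE = 0.1823/0.0641 = 2.85.
- Power is 80.3% (81.2% by the normal approximation), so the stated figure reproduces. The smallest n per arm that reaches 80% is 42 by the t calculation and 41 by the normal one.

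**Step 2: the caregiver ratio.**
- The ratio detectable with 80% power at 42 per arm and one-tailed alpha 0.05 is 1.173 at CV 0.3 and 1.292 at CV 0.5 (normal approximation). This matches the 1.17 to 1.29 of Hypothesis 1.2, so that range also appears to rest on 42 supporters per arm. The alpha of 0.05 is inferred from the match; the plan does not state it.
- At exactly 1.17, ln(1.17)/SE = 0.1570/0.0641 = 2.45. Power is 78.4% at the inferred 0.05 and 67.8% at the stated 0.025, both at full uptake.

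**Step 3: enrolment.** 42/0.90 = 46.7, so 47. 47/0.67 = 70.1, taken as 70. The whole step from 89 to 117 is used by Veteran non-completion.

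**Step 4: power by uptake**, ratio 1.20, one-tailed 0.025, CV 0.3. Case A takes supporters of completing Veterans only, with n = 42*u* per arm. Case B takes supporters of all enrolled Veterans, with n = 47*u* in DSW and 70*u*/1.07 in MFG. The design effect is 1 + (8 − 1) × 0.01 = 1.07.

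| Uptake | Case A | Case B |
|---|---|---|
| 100% | 80.3% | 89.6% |
| 90% | 76.0% | 86% |
| 80% | 70.8% | 81.9% |
| 70% | 64.8% | 76.5% |
| 60% | 58.0% | 70% |

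Crediting the MFG arm in case A with its 47 completers and the same design effect adds about one point: 81.2% at full uptake and 76.9% at 90%.

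For the ratio 1.17 at the inferred 0.05, case A gives 78.4%, 74.5%, 70.0%, 64.8% and 59.0% over the same uptakes.

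**The case against.** The strongest reply is that completing treatment is not the same as giving data. Section 1.1.15 separates participants who no longer want treatment from those who leave the study. Section 1.7 keeps subjects with partial data and plans comparisons of completers with non-completers. Supporters of Veterans who stop treatment could therefore still give burden scores at 12 and 15 months. The pool would then be 117, and 42 and 47 assessed supporters would need 42/47 = 89% uptake in DSW and 47/70 = 67% in MFG. This stands, and case B shows its effect. But the plan does not say that such supporters are followed, and case B assumes that none is lost, so it is an upper case.

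Two stronger readings are therefore tempting but unsupported. A reader might infer that 80% power holds only if every completing Veteran brings a completing supporter. That is roughly true in case A, but in case B about 80% uptake is enough. A reader might also infer that assessed supporters must be fewer than the 42 and 47. They are bounded by enrolled Veterans, not by completers. Nor is there an arithmetic error in the >80%: it reproduces, and what is missing is its premise about supporters.

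Other replies carry less weight:
- REORDER is meant to raise willingness to involve family, and a supporter need not be a relative. Both may help uptake, but neither gives a rate, so the lower rows of the table are illustrative.
- At ratio 1.20 with alpha 0.05, about 33 supporters per arm (33/42 = 79%) would give 80% power. The plan, however, ties its power to 0.025 and sets 1.17 for caregivers.
- Mixed models can use supporters with missed visits. They cannot supply data for a Veteran who has no supporter.

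**Conclusion.** The point holds as a matter of unsupported power, not of wrong arithmetic. Section 1.8 applies a Veteran count to family members, while the design allows Veterans without a supporter and gives no expected number of supporters.

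With 42 at the edge of what 80% requires, the result depends on who is followed. If only supporters of completing Veterans are assessed, 90% uptake already lowers power to about 76%, and 70% uptake to about 65%. If supporters of all 117 are assessed, more than 80% needs roughly 80% uptake. At the caregiver ratio of 1.17, 42 per arm does not reach 80% on either alpha, even with full uptake.

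These sizes rest on CV 0.3, a true ratio of 1, equal uptake in both arms and the plan's ICC of 0.01. Uptake itself is unknown, so the documents do not show what the caregiver power will be. They show only that the stated figure is not secured.

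**What to change.** In section 1.8:
- Stop applying the Veteran-based 42 per arm to family members.
- State the expected number of assessed primary supporters in each arm, allowing for Veterans without a supporter and for supporters who leave alone.
- State whether supporters of Veterans who stop treatment are followed to 12 and 15 months.
- Report caregiver-burden power separately on that basis, with its own ratio and its own alpha, for example as a table over 60% to 100% uptake.

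The cost is a few sentences and a small table, and a less favourable stated power for Hypothesis 1.2. Correcting the statement needs no extra enrolment. It does not raise the power itself; whether the corrected figure is acceptable for a primary outcome is then for the sponsor to decide.
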